## 13.4 Archiving

The University of Bristol will be the data custodian for all study data, irrespective of study site. All data will be held in Bristol and will conform to the University of Bristol's data security policy. All data will be held in compliance with GDPR and other relevant legislation. Further details are provided under 17.6 Data protection and patient confidentiality.

## 14.0 Safety

Medication review involves starting, stopping and otherwise changing medicines, and there is risk involved in this activity. However, this is a standard part of clinical practice, and we consider the safety risks posed by implementing the BRISMED Toolkit, over usual practice, to be very low. Nevertheless, out of an abundance of caution, we will conduct a pragmatic interim safety analysis, as well as allowing for spontaneous reporting where considered appropriate by the local principal investigator (PI).

### 14.1 Interim safety analysis

#### 14.1.1 Timing of interim analysis

The safety analysis will be conducted at 3 and 6 months. We have selected these time points as a compromise between providing adequate time for the intervention to have an impact (especially by 6 months), while providing enough time and opportunity (particularly at 3 months) to take action in the unlikely event of discrepancies in potential safety events occurring between the two arms.

#### 14.1.2 Data extraction

It is not feasible to use the ORCHID system or NHS England/digital to extract data for the safety analysis (detailed in 14.1.4 below) prior to the end of the study, so instead this will involve the 56 practices participating in the process evaluation. These practices will conduct a search in their clinical system of patients who have received a medication review in the previous 3 months. As patients will not have provided explicit consent, this search will only be used to generate aggregate patient numbers, and this will be used to assess rates of GP coding of adverse drug reactions, all-cause unplanned hospital admissions, and death between the two trial arms.

We have considered the ability to detect differences between the two arms of the study in these safety outcomes. Using similar numbers to the primary outcome sample size calculation with mean size of these practices 12514 (SD: 8473), 40% eligible and an ICC of 0.10 the table below shows the minimum detectable difference between the arms based on different baseline proportions of these outcomes and a power of 80% or 70%. The ICC uses a higher more conservative estimate than the primary outcome as only the practices within the process evaluation will contribute data to this safety analysis and is on the GP practice scale rather than the PCN scale. In all these cases, the minimum detectable difference is relatively large. We are not powered to detect relatively small differences in adverse event rates, but we anticipate 80% power to detect a ≤10% absolute increase in adverse event rate (assuming a baseline of event rate of ≤10%, and similar ICC and distribution of practice size to the main trial).

Baseline proportion	Detectable difference (80% power)	Detectable difference (70% power)
0.01	0.054	0.045
0.02	0.064	0.054
0.05	0.083	0.072
0.1	0.103	0.090

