#### 5.0 Trial eligibility criteria for practices

General practices using EMIS or SystmOne clinical systems, and contributing to the secure data processing environment of the nationally representative Oxford-Royal College of GPs Clinical Informatics Digital Hub (ORCHID), will be eligible to participate in the trial. Practices will only be included if they have not explicitly opted out of participating in the BRISMED study.

A subset of 56 practices (28 from each trial arm) will be recruited to the embedded mixed-methods process evaluation. Practices will be eligible to participate in the process evaluation if they have Accurx text messaging technology with ability for bulk text messaging enabled. This technology will be required for administration of patient surveys. All 56 practices conducting research activities as part of the process evaluation will be asked to complete the Organisation Information Document (OID), which is being used as the research agreement between the practice and the sponsor e.g. the University of Bristol.

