#### 8.0 Intervention design and delivery

#### 8.1 Overview of the intervention

The Bristol Medication Review (BRISMED) Toolkit intervention comprises components designed to facilitate more effective, thorough, and patient-centred medication review. This includes:

- · Model (BMR) for delivering a structured medication review
- Guidance on use of the model in clinical practice
- Primer document to empower patients to be more involved in their review
- Training materials for clinicians
- Templates for recording data in GP clinical systems
- Recommendations for practices on implementation

Intervention practices will be provided electronically with the BRISMED Toolkit. It will be left to individual practices how they implement the model (e.g. remote vs in-person; type of clinician conducting review; characteristics of patients invited to review, review frequency). The intervention makes no specific recommendations with respect to case-finding, and so participating sites will continue to identify patients who require a medication review in accordance with local policies. As such, the patients receiving a review as part of the intervention will be the same as those receiving a review as part of usual care.

Drawing on the COM-B model of behaviour change[27], we anticipate achieving change in medication review practice by modifying the capability, opportunity and motivation of clinicians to deliver reviews. Capability will be influenced by improving clinicians' knowledge and skills through provision of a clear and comprehensive model for conducting medication reviews alongside relevant training materials. Opportunity will be optimised by aligning the intervention to usual practice (with familiarity helping to ensure legitimacy and reduce barriers to adoption), using a model of review which aligns with standard consulting behaviour and is flexible for different clinicians' approaches, providing guidance and recommendations to support practices and PCNs to identify optimal approaches to implementation, and ensuring access to relevant resources (provision of a clinical IT template, primer document, and website providing easy access to supporting materials). Motivation will be enhanced through education about the importance of medication reviews, quarterly reminder information sent to intervention practices, continuous professional development (CPD) certificates for completing training, and reimbursement of training time.

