## 14.1.4 Analysis

The analysis of the interim safety measures will use the same approach as the main analysis for the primary outcome measure (section 11.3.2). That is random effects Poisson regression on the practice scale to explore the rates of the safety measures within each GP practice over the first 3 and also the first 6 months. The number of patients potentially eligible for review at each GP site will be used as the offset term.

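### The interim safety analysis counts events among recently reviewed patients but offsets by all patients eligible for review, so its arm ratio mixes review activity with harm; the month-6 search window also does not match the stated period

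*Protocol*

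**What the plan says.** Protocol section 14.1.2 explains that ORCHID and national data cannot be extracted for safety before the study ends. The interim comparison therefore uses the process evaluation practices, 28 in each arm. They are to "conduct a search in their clinical system of patients who have received a medication review in the previous 3 months". The search returns aggregate counts only, and from these the two arms are compared on coded drug reactions, unplanned admissions from any cause, and deaths.

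Section 14.1.4 applies the primary-outcome method, a random effects Poisson model at practice level, to the "rates of the safety measures within each GP practice over the first 3 and also the first 6 months". On the denominator it says: "The number of patients potentially eligible for review at each GP site will be used as the offset term".

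Section 8.1 bears on whether review activity can differ by arm. It leaves to each practice the "characteristics of patients invited to review, review frequency". It also says that the intervention makes no case-finding recommendation and that the patients reviewed will be the same as under usual care.

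**The concern.** The events come from one group of patients and the offset describes a larger one. A rate built this way rises when a practice reviews more of its eligible patients, even if no reviewed patient is at higher risk. It falls when the practice reviews fewer.

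The offset appears to be carried over from section 11.3.2. There it fits, because the primary outcome is assessed at practice level and is not restricted to patients with a recent review.

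The time windows raise a second, smaller problem. A 3-month look-back at month 6 finds patients reviewed in months 4 to 6, whereas section 14.1.4 asks for a rate over the first 6 months.

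This is the only between-arm safety comparison planned for the Data Monitoring Committee during delivery (sections 14.1.2, 14.3 and 15.6). Spontaneous reports cannot stand in for it, because Appendix 2 states that a control practice cannot have a related reaction. A ratio that moves with review activity could prompt a false alarm or give false reassurance.

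**Working it through.** **1. The protocol's detectable differences.** Inputs from section 14.1.2: mean practice size 12,514 (SD 8,473), 40% eligible, ICC 0.10. There are 28 practices per arm. A two-sided alpha of 5% is assumed, carried over from section 11.1.

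- Eligible patients per practice: m = 0.40 × 12,514 = 5,006. CV = 8,473 / 12,514 = 0.677.
- Design effect: 1 + ((1 + CV²)m − 1) × ICC = 730.9.
- Effective sample size per arm: 28 × m / 730.9 = 191.7.

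| Baseline | Protocol, 80% / 70% power | Recomputed (pooled normal) | Recomputed (t, 54 df), 80% |
|---|---|---|---|
| 0.01 | 0.054 / 0.045 | 0.0538 / 0.0449 | 0.0546 |
| 0.02 | 0.064 / 0.054 | 0.0631 / 0.0535 | 0.0640 |
| 0.05 | 0.083 / 0.072 | 0.0820 / 0.0708 | 0.0832 |
| 0.10 | 0.103 / 0.090 | 0.1022 / 0.0891 | 0.1034 |

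The table reproduces, and it takes the eligible patients as the population at risk.

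**2. Share of that population that is searched.** Section 14.1.3 gives about 1,000 reviews per 3 months on a list of 10,000. Eligible patients number 0.40 × 10,000 = 4,000, so the share is 1,000 / 4,000 = 25%, counting each review as one patient. A table entry of 0.01 rising to 0.064 per eligible patient then means 0.04 rising to 0.256 per reviewed patient.

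**3. What the model estimates.** In each arm:

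events / eligible = (reviewed / eligible) × (events / reviewed)

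The arm rate ratio is therefore (ratio of shares reviewed) × (ratio of risks per reviewed patient). This is an identity and needs no assumption. The review ratios below are assumptions, because the protocol gives none by arm.

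| Review-share ratio (assumed) | Risk ratio per reviewed patient | Rate ratio with the eligible offset |
|---|---|---|
| 1.00 | 1.00 | 1.00 |
| 1.10 | 1.00 | 1.10 |
| 1.20 | 1.00 | 1.20 |
| 1.50 | 1.00 | 1.50 |
| 0.80 | 1.25 | 1.00 |
| 0.75 | 1.33 | 1.00 |

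**4. The month-6 window.** Assume N patients reviewed evenly over 6 months, with events counted from review to the search date. The protocol states no event window, so this too is an assumption.

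- Post-review time by month 6: N × 3 = 3N person-months.
- Month-3 search: 0.5N × 1.5 = 0.75N. Month-6 search: 0.5N × 1.5 = 0.75N.
- Both searches together: 1.5N of 3N, or 50%.
- The missing 1.5N is months 4 to 6 in patients reviewed in months 1 to 3 (0.5N × 3).

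**5. Precision with a reviewed-patient denominator.** With m = 0.10 × 12,514 = 1,251 and the same CV and ICC, the design effect is 183.4 and the effective sample size is 191.0 per arm. Detectable differences at 80% power (pooled normal) are 0.0539, 0.0632, 0.0822 and 0.1024. They hardly change, because the ICC term dominates.

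**The case against.** The strongest reply is the section 8.1 statement that the same patients will be reviewed in both arms. If that holds, the mismatch is a scale factor common to both arms and the rate ratio is unbiased. This premise should be weighed, but it does not settle the matter. The same section leaves review frequency and patient selection to practices, and gives intervention practices reminders, paid training time and a recording template. Sections 7.2 and 10.4 treat review rates as something to measure. Nothing in section 14 adjusts for them.

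It can also be said that the section 14.1.2 search was meant to supply the denominator. Section 14.1.4 names a different one, so the two sections conflict on that reading as well.

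Several limits on the point stand:

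- A reader might infer that the arms will differ in review activity and that the comparison is biased. The documents give no arm-specific review rates, so they show only that the comparison is unprotected.
- A reader might infer that patients reviewed in months 1 to 3 are lost altogether. The month-3 search includes them. What is missed at interim is their later events, and the protocol does not say how a 6-month count would be assembled from the two searches.
- A reader might infer that the power sentence, "we anticipate 80% power to detect a ≤10% absolute increase in adverse event rate", is a material error. It is rounding. The table gives 10.3 points at a 10% baseline, where 10 points has about 78.6% power, and the text admits that small differences cannot be detected.
- Unplanned admissions, medication-related admissions and mortality are collected later in about 800–900 practices (section 7.2). The committee also advises on how safety data are presented (section 15.6). The effectiveness analyses are untouched.

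**Conclusion.** The point holds. Sections 14.1.2 and 14.1.4 define different populations for events and offset, and the estimated arm ratio is the product of a review-share ratio and a harm ratio. It is unbiased for harm only if both arms review the same share of eligible patients, which the protocol asserts but does not secure. The distortion equals the review-share ratio, whatever that proves to be. The values of 1.20, and of 1.33 appearing as 1.00, are illustrations.

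The window conflict holds in a smaller form. The month-6 search cannot by itself yield the 6-month rate, and later events in the earliest reviewed patients are missed at interim. That loss is half of post-review time under even reviewing and the counting rule assumed above.

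The detectable-difference table is arithmetically sound and is not part of the fault. The passages should be reconciled before the interim searches are run, because they determine what the committee sees.

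**What to change.** Preferred: rewrite the section 14.1.2 search so that practices count the three event types in all eligible adults from the start of delivery, at month 3 and again at month 6, and keep the section 14.1.4 offset. Events, offset and period then agree, and the randomised comparison is preserved. The cost is dilution by unreviewed patients. For example, with 25% reviewed, equal background risk in reviewed and unreviewed patients, and a risk ratio of 1.33 confined to the reviewed, the ratio among all eligible adults would be 0.25 × 1.33 + 0.75 × 1.00 = 1.08.

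Alternatively or in addition: use the number of reviewed patients returned by the same search as the offset. At month 6, search back to the start of delivery and count events dated after the review. Report the share reviewed by arm beside the result, and state that this analysis conditions on a post-randomisation event, so it can be confounded if the arms select different patients for review.

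The change is to the practice search instruction and to the offset and period wording in section 14.1.4, handled as an amendment under section 17.3. It needs no extra practices and no new data source, and the returns remain aggregate counts. The power sentence may be aligned with the table's 5.4 to 10.3 points, but this is optional.

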## 14.1.3 Categorisation of safety events

For an average practice with list size 10,000, this equates to approximately 1,000 medication reviews being undertaken in a 3-month period. The very nature of medication reviews includes the explicit identification of potential safety concerns, but these numbers make it entirely unfeasible to conduct a formal categorisation of safety events. Local PIs will therefore not be asked to review events to attribute seriousness, intensity, relatedness and expectedness.

## 14.1.4 Analysis

The analysis of the interim safety measures will use the same approach as the main analysis for the primary outcome measure (section 11.3.2). That is random effects Poisson regression on the practice scale to explore the rates of the safety measures within each GP practice over the first 3 and also the first 6 months. The number of patients potentially eligible for review at each GP site will be used as the offset term.

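### The interim safety model counts events in reviewed patients but offsets by all eligible patients, so its rate ratio also carries any between-arm difference in review volume

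*Protocol*

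**What the plan says.** Protocol section 14.1.2 explains that central data cannot be extracted before the end of the study, so interim safety data come from the 56 process evaluation practices, 28 per arm. The search is defined by receipt of a review: "These practices will conduct a search in their clinical system of patients who have received a medication review in the previous 3 months". It yields aggregate numbers only. Their purpose is given as follows: "this will be used to assess rates of GP coding of adverse drug reactions, all-cause unplanned hospital admissions, and death between the two trial arms".

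Section 14.1.4 applies the approach of the primary analysis (section 11.3.2), a random effects Poisson regression on the practice scale, to the first 3 and the first 6 months. It sets the denominator: "The number of patients potentially eligible for review at each GP site will be used as the offset term". The search described in 14.1.2 is not said to return that number.

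On volume, section 14.1.3 says that for a list of 10,000 "this equates to approximately 1,000 medication reviews being undertaken in a 3-month period". Section 8.1 leaves implementation to each practice, including "characteristics of patients invited to review, review frequency". It also says that sites will go on identifying patients under local policy and that those reviewed will therefore be the same as under usual care.

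**The concern.** In a Poisson model the offset should count the people in whom the events could have been recorded. Here events can be recorded only in patients who have had a review, while the offset counts everyone who might have one. The model then estimates events in reviewed patients per eligible patient. That is a product of two things: the risk among reviewed patients, and the share of eligible patients reviewed so far. Only the first is safety; the second is throughput.

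The same offset suits the primary analysis, because the primary outcome is not described as restricted to reviewed patients. The mismatch arises when the sentence is carried over to a search that is restricted in this way.

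At stake is the only between-arm comparison of event rates planned while action is still possible. Section 14.1.3 drops event-by-event categorisation, section 14.2 notes that the earlier IMPPP trial received no spontaneous reports, and Appendix 2 states that a control practice cannot have a related reaction. If the interim ratio misleads, little else in the plan would correct it.

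**Working it through.** **Inputs from the protocol.** 28 practices per arm; mean list 12,514 (SD 8,473); 40% eligible; ICC 0.10 (14.1.2). About 1,000 reviews per 3 months for a list of 10,000 (14.1.3). Two-sided alpha of 5% is assumed, as in 11.1, because none is stated for safety.

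**1. The printed table.** Eligible patients per practice m = 12,514 × 0.40 = 5,006. CV = 8,473 / 12,514 = 0.677, so 1 + CV² = 1.458. Design effect = 1 + (1.458 × 5,006 − 1) × 0.10 = 731. Effective n per arm = 28 × 5,006 / 731 = 192. Detectable increases at 80% power:

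| Baseline | Printed | Pooled normal | t, 54 df |
|---|---|---|---|
| 0.01 | 0.054 | 0.0538 | 0.0546 |
| 0.02 | 0.064 | 0.0631 | 0.0640 |
| 0.05 | 0.083 | 0.0820 | 0.0832 |
| 0.10 | 0.103 | 0.1022 | 0.1034 |

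The table reproduces on its inputs.

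**2. Size of the mismatch.** Eligible in a list of 10,000: 10,000 × 0.40 = 4,000. Reviewed in 3 months: 1,000. Share = 1,000 / 4,000 = 25%, so the offset is about four times the group in which events are counted.

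**3. What the model estimates.** Let r be the event rate per reviewed patient and s the share of eligible patients reviewed. Expected events per eligible patient = r × s, so

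expected rate ratio = (r_int / r_ctl) × (s_int / s_ctl).

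A share common to both arms, 25% or any other, cancels. A difference in share does not:

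| True ratio among reviewed | Review-volume ratio | Ratio from the model |
|---|---|---|
| 1.00 | 1.00 | 1.00 |
| 1.25 | 1.00 | 1.25 |
| 1.25 | 0.80 | 1.00 |
| 1.00 | 1.25 | 1.25 |
| 1.00 | 0.80 | 0.80 |
| 1.50 | 0.70 | 1.05 |

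The volume ratios are illustrations; the protocol gives none. The products need no assumption about event rate or ICC.

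**4. Simulation.** 28 v 28 practices were drawn with the protocol's list sizes and a 25% control-arm review share. Assumed, not in the documents: a 5% event rate among reviewed patients, between-practice rate CV 0.3, review-share log-SD 0.2. There were 400 runs, with a negative binomial model standing in for the random effect. Rejection rates are at two-sided 5%.

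| Scenario | Eligible offset: ratio, rejection | Reviewed offset: ratio, rejection |
|---|---|---|
| No harm, equal volume | 1.00, 5% | 1.00, 3% |
| No harm, 25% more reviews | 1.25, 57% | 1.00, 5% |
| No harm, 20% fewer reviews | 0.80, 54% | 1.00, 3% |
| True 1.25, 20% fewer reviews | 1.00, 5% | 1.25, 72% |

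The ratios agree with step 3. The rejection rates depend on the assumptions.

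**5. Power after matching the denominator.** With m = 5,006 × 0.25 = 1,251 reviewed patients, effective n per arm is 191 and the detectable increase from 10% is 0.1024 (pooled), against 0.1022 with m = 5,006. Almost nothing is lost, because the ICC, not the cluster size, drives the design effect.

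**The case against.** The strongest reply is that bias needs review volume to differ by arm, and section 8.1 points the other way: the toolkit makes no case-finding recommendation, local policies continue, and the same patients are expected to be reviewed. Section 5.2.1 adds that little or no extra resource is needed. Nothing in the protocol predicts fewer or longer reviews under the toolkit. This stands, and it makes the bias conditional. It does not remove it. Section 8.1 also leaves review frequency to practices, aims to change clinicians' motivation and sends quarterly reminders to intervention practices, and section 10.4 measures review rates as an implementation result. Equal volume is an expectation that the trial itself sets out to check.

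A second reply is that the obvious repair has its own flaw: being reviewed happens after randomisation, so if the arms review different kinds of patient, a reviewed-patient offset can be biased too. This also stands, and is why review counts should be shown by arm and why a second repair is offered below.

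A third is that the analysis is modest by design. The protocol says it cannot detect small differences, the DMC also sees spontaneous reports, and it advises on how safety data are presented. That limits the consequences but does not align the two sections.

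A reader might also infer that the detectable differences are badly wrong. A 10% risk among reviewed patients is 10% × 0.25 = 2.5% of eligible patients. The table's formula at 2.5% with ICC 0.10 gives 0.067, or 0.067 / 0.25 = 27 points among reviewed patients. The documents do not support that reading, because the ICC cannot stay at 0.10 when every practice's rate is scaled by the same factor. At 10%, ICC 0.10 means a between-practice variance of 0.10 × 0.10 × 0.90 = 0.009. Scaled by 0.25² this is 0.00056, and 0.00056 / (0.025 × 0.975) = 0.023. At ICC 0.023 the detectable increase is 0.0264, or 10.6 points among reviewed patients, close to the printed 10.3.

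**Conclusion.** The mismatch is explicit: sections 14.1.2 and 14.1.4 define the numerator and the denominator on different groups, and no other section reconciles them. The interim rate ratio equals the true ratio among reviewed patients times the between-arm ratio of review shares. Its error is exactly that second factor: none if volume is equal, a factor of 0.80 with 20% fewer intervention reviews, a factor of 1.25 with 25% more. This result rests only on the two sections as written. Whether bias occurs depends on review volumes that are not yet known. Absolute rates per eligible patient would understate the risk among reviewed patients about fourfold at 3 months, whatever happens between arms.

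The point does not extend to the printed power figures, which are essentially unaffected, or to the primary analysis, whose outcome is not described as limited to reviewed patients. One related gap belongs with it: the search looks back 3 months, while the model covers the first 3 and the first 6 months. Adding two 3-month searches could count a patient twice. A second search alone would miss patients reviewed only in the first quarter.

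**What to change.** Make numerator and denominator the same people in section 14.1.4, by one of two routes.

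(a) Keep the search and use the log of the number of reviewed patients it returns as the offset. Report the number reviewed by arm beside each safety ratio, and state that this conditions on a post-randomisation event, so a change in who is reviewed could still bias the comparison.

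(b) Widen the search in section 14.1.2 to count events in all patients eligible for review, and keep the present offset. This stays closer to intention to treat.

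Under either route, define the 6-month search so that it covers the whole 6 months and counts each patient once.

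Route (a) costs a sentence in 14.1.4 and a clarified window in 14.1.2. It needs no new kind of data and leaves the detectable difference almost unchanged (0.1024 against 0.1022 at a 10% baseline). Route (b) needs a broader search in the 56 practices.
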